Randomization: Participants will be individually randomized to either iTRAC-SRP or waitlist control after baseline, following consent. Per recommendations for achieving between-group comparability in clinical trials,¹⁰⁵ randomization will be stratified by school and gender and blocked using predetermined size-4 blocks. Individual randomization avoids nesting of conditions within schools by each school hosting both conditions, which is feasible given individual program completion. We considered randomization by school, but a group randomized design would require >30 schools to achieve adequate power. Minor concern exists that teens from different conditions may discuss the intervention; as in Project TRAC, we will measure this “cross-talk” via assessment. Project staff will log participants into the password-protected site to avoid outside access. Accessibility will be an ultimate goal of iTRAC, but use will be monitored during the study to control for dose.

Intervention Condition: iTRAC-SRP will consist of eight, approximately 45-minute, “gamified” digital modules of 4-6 activities (games, videos, etc.). Teens will complete modules in after-school supervised groups. Students will be allowed to complete 1-2 modules each week (total intervention completion time 4-8 weeks); project staff will be present at each school at least three days per week, allowing flexible scheduling/attendance. No instruction is needed to use the program. Teens will come to a common area (e.g., classroom, library) where they will be provided a project tablet connected to Wi-Fi. They will have an individual account for the program (password controlled by project staff to prevent outside use), by which they will resume where they left off at the previous module (thus allowing flexible administration and breaks, as needed). We have chosen this strategy for the research for pragmatic reasons; after-school formats are common in schools, and this time, location, and format were successful in TRAC and iTRAC. However, we recognize that the program may be administered differently (e.g., during class time, in waiting rooms, or at home) once it is commercialized.

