Data Analysis: A more detailed description of the analytic plan and justification for power calculations is presented in Section 4.4 Statistical Design and Power, including approaches to evaluate model assumptions, potential imbalance between treatment groups in baseline characteristics, and missing data. Analysis of covariance will be used to evaluate changes in self-efficacy for sexual risk prevention skills over 6-months post intervention with baseline as a covariate. All participants who were randomized will be included in all analyses (i.e., intent-to-treat). The size of the treatment effect will be estimated using standardized mean differences. The same approach will be used to evaluate sexual health knowledge and emotional competencies. Sexual behaviors (number of sexual behaviors, number of condomless sex acts) will each be aggregated across the two- and six-month follow-up assessments and analyzed using generalized linear models with log link functions and negative-binomial distributions for behavioral counts that are expected to follow a zero-altered count distribution. Exploratory analyses: Mediation: Causal mediation models will be used to test how much of the treatment effect is accounted for by measures of emotional competencies and sexual attitudes. Causal mediation provides a general framework for evaluating mediation in both linear and nonlinear models, including count outcomes¹. Moderation: To better understand who is benefiting most from the intervention we will use causal random forests, a non-parametric data-mining procedure². Although this principled exploratory approach cannot definitively define subgroups, it has better statistical properties than looking at individual moderators and will help suggest subgroups that differ in terms of their response to the intervention.

Power and Sample Size: This trial was powered to the primary and other continuously scaled outcomes (self-efficacy, knowledge, and emotional competencies). With 120 participants, this study is powered at .80 to detect moderate effect sizes (standardized mean difference $d \geq .47$). The power analysis was run using the R package simstudy v0.2.1 and assumed a two tailed type-1 error rate of .05 and a correlation between baseline and

the 6-month outcome of $r=.6$. Effect sizes from our previous work with TRAC and iTRAC showed effect sizes ranging from .20 to .70.

Deliverable: A summary report of the trial data will be created and submitted for publication.

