144. Office of Disease Prevention and Health Promotion. *Healthy People 2030*. <https://health.gov/healthypeople/objectives-and-data/data-sources-and-methods/data-sources/national-survey-family-growth-nsfg>

STATISTICAL DESIGN AND POWER

Data preparation: Relevant tests of model assumptions will be evaluated with all analyses, and appropriate corrections for problems in distributions will be implemented. Because even small and statistically non-significant between condition differences in baseline characteristics can adversely affect treatment effect estimates, we will use inverse probability of treatment weights (IPTW) to adjust for potential imbalance between conditions^{1,2}. Covariate balancing propensity scores³ will be used to generate the weights and the model will include demographics and baseline measures of primary outcomes, secondary outcomes, exploratory outcomes, moderators, and mechanisms. The effectiveness of the IPTWs will be evaluated by looking at the average and largest effect sizes for between condition differences prior-to and following weighting. We will also examine the positivity or common support assumption required for IPTW by visually examining the overlap in propensity score distributions for each condition. This assumption is likely to hold in the context of a randomized trial.

Missing data: Based on previous projects, we expect 10% attrition by the end of the 6-month follow-up. We will use fully conditional multiple imputation (a.k.a., multiple imputation using chained equations [MICE]⁴) to address bias introduced by missing data. MICE was selected because it can handle outcomes with different statistical distributions (i.e., binomial, Poisson, normal), it can be applied to a large number of variables, and it has solid performance in simulation studies⁴. This approach assumes data are missing at random (MAR).

Primary Outcome: The primary outcome of the RCT will be Self-efficacy for Sexual Risk Prevention at the 6-month follow-up. All participants who were randomized will be included in all analyses (i.e., intent-to-treat). This outcome will be assessed using an analysis of covariance with baseline included as a covariate.

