Secondary Outcomes: Secondary outcomes include sexual health knowledge, abstinence attitudes, sexual behaviors, and condomless sex acts. Sexual health knowledge will be analyzed like the primary outcome. Sexual behaviors will be summed across the follow-up assessments. Multiple imputation will be used to address missing assessments and the summation will occur within each imputation to ensure that missing assessment are appropriately counted. These data are expected to be zero-altered and will thus be analyzed using generalized linear models with a negative binomial distribution and a log link function. Condomless sex acts will be analyzed like sexual behaviors.

Mechanisms: Measures of mechanisms include theoretically important emotional competencies (e.g., emotion regulation, emotion recognition, distress tolerance) that mediate risk as measured by self-report, performance measures, and parent report. These outcomes will be assessed at the 2-month and 6-month follow-ups using analysis of covariance like for the primary outcome.

Power and Sample Size: This trial was powered to the continuously scaled outcomes (self-efficacy, knowledge, and emotional competencies). With 120 participants, this study is powered at .80 to detect moderate effect sizes (standardized mean difference $d \geq .47$). The power analysis was run using the R package simstudy v0.2.1 and assumed a two tailed type-1 error rate of .05 and a correlation between baseline and the 6-month outcome of $r=.6$. Effect sizes from our previous work showed effect sizes ranging from .20 to .70.

Exploratory analyses of mediation and treatment modifiers: **Mediation:** Causal mediation will be used to evaluate whether treatment-related change in self-efficacy was attributable to change in mechanisms. Causal mediation was selected because the framework can handle mediators and outcomes with non-normal distributions such as a binary outcome⁸. Mediation analyses will be run for each of the hypothesized mechanisms. **Moderation:** To better understand who is benefiting most from the intervention we will use causal random forests, a non-parametric data-mining procedure⁹. Although this principled exploratory approach cannot definitively define subgroups, it has better statistical properties than looking at individual moderators and will help suggest subgroups that differ in terms of their response to the intervention. Power was not calculated for these exploratory analyses.

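### Propensity weights built from every baseline domain (about 25 terms for 120 participants) leave the 5% test level dependent mainly on an unstated standard error; a short direct ANCOVA that includes the randomization strata avoids this

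*Combined protocol and SAP*

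**What the plan says.** The Data preparation paragraph adopts weighting outright, with no trigger such as an observed imbalance. The weights come from CBPS, and "the model will include demographics and baseline measures of primary outcomes, secondary outcomes, exploratory outcomes, moderators, and mechanisms". Only domains are named. One of them, exploratory outcomes, is a label that no outcome carries elsewhere in the plan. Two checks are planned: between-arm effect sizes before and after weighting, and a look at common support "by visually examining the overlap in propensity score distributions for each condition". On common support the plan adds: "This assumption is likely to hold in the context of a randomized trial". It gives no action if either check looks poor, and it states no estimand, CBPS variant, trimming rule or standard error.

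The Primary Outcome paragraph of the same section does not mention weights: "This outcome will be assessed using an analysis of covariance with baseline included as a covariate". The link comes from the Data Analysis paragraph of the Phase 2c description, which sends the reader to this section for "potential imbalance between treatment groups in baseline characteristics, and missing data".

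Under Randomization, "randomization will be stratified by school and gender and blocked using predetermined size-4 blocks". The stated ANCOVA includes neither factor. Gender may fall under demographics in the propensity model; school is named in neither place.

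The Power and Sample Size paragraph says "With 120 participants, this study is powered at .80 to detect moderate effect sizes", at d of .47 or more, two-sided alpha .05 and a baseline-outcome correlation of .6. It does not mention weighting.

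**The concern.** Randomization makes the true assignment probability one half for everyone. The fitted score is another matter: with about 25 terms and 60 per arm, the model picks up chance differences and the weights vary accordingly. Two things then happen. The variable weights add noise. If the balanced covariates predict the outcome, balancing them removes noise. Common standard errors do not follow both effects, so the nominal 5% test can run above or below 5%, and nobody can say which until the standard error is fixed. What is at stake is whether the primary p-value means what it says, and whether the standard error could be chosen after the data are seen. Omitting school and gender, on which allocation was balanced, is a smaller related loss.

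**Working it through.** **Inputs from the documents.** N = 120 (60 per arm, inferred from blocks of 4), d = .47, alpha .05 two-sided, r = .6, four schools by two genders. **Assumed:** five demographics; covariates inter-correlated .3; extra covariates explaining 0, 20 or 40% of the outcome variance left after baseline. The documents give no prognostic figure, so a range is shown.

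**Stated power.** For unweighted ANCOVA, SE = sqrt(4/120 × (1 − .6²)) = sqrt(.02133) = .146, and .47/.146 = 3.22. Power is Φ(3.22 − 1.96) = .896 (.891 with the t distribution), and the effect detectable at .80 power is 2.80 × .146 = .41. The stated .80 at .47 is therefore conservative for this ANCOVA and is not reproduced by it. The documents do not say whether the power simulation included weights, and nothing below depends on this.

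**Term count, one total per scale.** Demographics 5 (assumed) + primary 1 + secondary 4 (knowledge, abstinence attitudes, sexual behaviors, condomless acts) + non-sexual risk items 1 (assumed to be the exploratory outcomes) + moderators 5 + mechanisms 9 (five self-report scales, two performance tasks, and the self-regulatory inventory by adolescent and by parent) = 25. That is 120/25 = 4.8 participants per term.

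**Type I error by simulation.** N = 120, 25 terms, permuted blocks of 4 within strata, weighted ANCOVA on baseline; 4,000 trials, so the Monte Carlo SE at 5% is sqrt(.05 × .95/4000) = .003. Figures in brackets are from a separate simulation.

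| Analysis | 0% | 20% | 40% |
|---|---|---|---|
| Just-identified, ordinary weighted SE | .092 (.105) | .062 (.065) | .033 (.036) |
| Just-identified, robust SE (HC1), weights fixed | .057 (.061) | .033 (.032) | .015 (.016) |
| Just-identified, stacked sandwich | .15 | .15 | .15 |
| Just-identified, bootstrap refitting the weights* | .040 | .040 | .040 |
| Over-identified, ordinary weighted SE | .076 | .052 | .030 |
| Over-identified, HC1 | .057 | .037 | .018 |

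*400 trials, Monte Carlo SE about .01; 24% of resamples failed to converge.

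Unweighted ANCOVA with 10 terms (baseline, 3 for school, 1 for gender, 5 covariates; 8,000 trials per setting) gave .045-.055 (separate simulation: .044-.052).

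Median effective sample size was 89 (just-identified) and 102 (over-identified) of 120. Under just-identified CBPS, 15% of fitted scores lay outside .1-.9.

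**Why the standard error drives this.** The rejection rate is roughly 2 × [1 − Φ(1.96 × mean SE / true SD)]. In a further just-identified run of 400 trials:
- No prognostic value, true SD .1725. Ordinary SE .1455: 1.96 × .843 = 1.65, giving .098. Robust SE .1673: 1.90, giving .057. Stacked SE .1255: 1.43, giving .154.
- Extra covariates explaining .30 of total outcome variance (.30/.64 = 47% of residual), true SD .1262. Ordinary SE .1453: 2.26, giving .024. Robust SE .1673: 2.60, giving .009.

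The true SD falls from .1725 to .1262, while the ordinary and robust SEs hardly move.

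**CBPS variant and estimand.** Under HC1 the two variants differ by 0, .004 and .003. The estimand matters for feasibility: in a separate set of runs, just-identified weights targeting the treated had a solution in only 38% of trials.

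**Power at d = .47, N = 120** (0/20/40%). Just-identified with HC1: .78/.80/.84. Over-identified with HC1: .83/.85/.88. Ten-term ANCOVA: .87 if the list captures nothing; .90 or .94 if it captures half or all of 20%; .93 or .98 for half or all of 40%.

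**Strata.** If school and gender explain 5/10% of residual variance, ANCOVA without them has type I error .043/.038 and power .89/.90; with them, .049/.048 and .90/.92.

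**Rare items (illustrative, just-identified only).** An item reported in exactly one arm cannot be balanced exactly. The chance is 2(1 − p)^60 − 2(1 − p)^120, which is .27 at p = .03. That 3% is the national figure for intercourse before age 13 in the Significance section, not this trial's baseline rate; the trial's measure also covers broader behaviors.

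**The case against.** A reader might infer that the planned weighting inflates type I error as such. The documents do not support that. Inflation needs an ordinary weighted standard error with weakly prognostic covariates, or a stacked sandwich, and the plan names neither. Zero prognostic value is the extreme case, since the model includes sexual knowledge, abstinence attitudes and emotional self-efficacy. Away from it, the ordinary and robust tests are near nominal or conservative. A reader might also blame the choice of CBPS variant; under a robust standard error that choice barely matters.

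Nor does it follow that weighting leaves the trial underpowered. Over-identified CBPS with HC1 meets the stated .80 throughout, and just-identified CBPS with HC1 gives .78-.84. The plan expects dropout ("we expect 10% attrition by the end of the 6-month follow-up") but will impute, and imputation was not simulated, so no attrition-adjusted power is offered here. A larger term count, from splitting scales into subscales or items, is possible but not stated.

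It can fairly be said that the weights may not be meant for the primary ANCOVA, since its own sentence omits them. That stands as an ambiguity. The cross-reference and the stated purpose of protecting treatment-effect estimates make weighting the natural reading. Broad weighting can also gain precision when the covariates are strongly prognostic, and that stands in full. Finally, the opening note says Phase 2 is included for reference only; this affects timing, not substance.

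**Conclusion.** The point holds in a limited form. With about 25 terms for 120 participants, the level of the weighted test runs from about 1.5% to about 15%, depending mainly on a standard error that the plan does not state and on prognostic strength that the documents do not give. Some combinations are acceptable, but the plan does not choose one. A short direct ANCOVA stays at about 5% without that choice and has power of about .87 or more at d = .47 with N = 120. The omission of school and gender is real but small: about .01-.02 in power if they explain 5-10% of residual variance. The conclusion rests on the 25-term count, the assumed covariate correlation and prognostic range, complete outcomes, and the inference that the weights reach the primary analysis. It should be fixed; it is not evidence that the design is unsound.

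**What to change.** Make the primary analysis an unweighted ANCOVA on the baseline score, school, gender and a short prespecified list of prognostic covariates, about 10 terms in all. State explicitly that it is unweighted. Keep broad weighting as a sensitivity analysis and specify it: the term list (including what counts as an exploratory outcome), the estimand, the CBPS variant, a standard error checked by simulation at this sample size and number of terms, and an action if overlap is poor or effective sample size is low. Leave rare baseline sexual-behavior items out if exact balance is required. Restate power for the analysis chosen, allowing for the expected attrition under the planned imputation. At minimum, add school and gender to the stated ANCOVA.

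The cost is SAP wording only, on data already planned, and it can be settled before the randomized phase. The downside is some precision if the broad set is strongly prognostic and the short list misses much of it. At 40% of residual variance, the variance relative to baseline-only ANCOVA is .78 for broad over-identified weighting, against .85 for a short list capturing half and 1.05 for one capturing none. Chance imbalance outside the list would be reported rather than weighted away.

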Treatment Mechanisms (Mediators): *Emotion regulation* will be measured via self-report, performance measures, and parent observation. Teacher measures were considered; our experience in Project TRAC was that students changed teachers too frequently for long-term follow-ups and that short-term follow-ups (2 months) did not provide time for the ER skills learned for risk situations to generalize to non-risk settings, like the classroom⁴⁸. **Self-report:** The Difficulties in Emotion Regulation Scale (36 items¹²⁰) uses six subscales (e.g., lack of emotional awareness, limited access to ER strategies; all $\alpha \geq .80$) to assess perceptions of skill in ER based on Linehan's theoretical work.¹²¹ The Affect Dysregulation Scale (6 items¹²²) assesses the frequency of difficulties with ER ($\alpha = .72$), and is shown to be related to adolescent risk behaviors.¹²² The Emotion Regulation Behaviors Scale- Revised (9 items¹²³) measures use of the specific emotion regulation strategies taught in iTRAC ($\alpha = .73$). The emotional self-efficacy subscale of the Self-Efficacy Questionnaire for Children (8 items¹²⁴) assesses perception of one's ability to cope with negative emotions ($\alpha = .83$). It has been shown to be valid, reliable, and related to risk behaviors among adolescents.¹²⁴ The Implicit Theories of Emotions for Children- Self subscale (6 items)¹²⁵ is based on Dweck and colleagues' work on implicit theories of intelligence¹²⁶ and Tamir's adult measure of emotion malleability. ENREF 146¹²⁷ It assesses adolescents' beliefs about the controllability of their emotions ($\alpha = .86$). All of these measures were successfully used in the iTRAC study. **Performance measures:** a) Diagnostic Analysis of Nonverbal Accuracy-2⁵⁰ (DANVA2) is a computer-based measure that asks participants to identify the emotion of facial expressions displayed in photographs. The measure has shown one-month test-retest reliability over .8⁵⁰ and had an alpha of .83 in Project TRAC. b) Behavioral Indicator of Resiliency to Distress (BIRD)¹²⁸ is a 5-minute computerized distress tolerance task in which participants are given the option to quit at any time. It generates a score of time spent persisting on a frustrating task that provides negative feedback (aversive noise) when users fail at the task.¹²⁸⁻¹³⁰ **Parent report:** The Adolescent Self-Regulatory Inventory (29 items)¹³¹ measures perceptions of adolescents' abilities to regulate over the short-term and long-term, separately; both adolescents and parents will complete it about the adolescent ($\alpha = .75-.90$). Parents will complete this measure at baseline and 6-months, to reduce burden.

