
Treatment Moderators: Demographic information will be collected, allowing for analysis of demographic factors, including sex as a biological variable, as moderating influences of treatment effects. Self-Rating Scale for Pubertal Development (PDS; 5 items)¹³² will be used, as pubertal status and sexual activity are related. The PDS uses gender-specific items to assess physical maturation. It is reliable ($\alpha = .67$) and strongly correlated with pediatrician-rated physical development.¹³² The Columbia Impairment Scale (CIS; 13 items)¹³³ provides a global measure of functional impairment with good reliability and validity.^{131, 133} A score of ≥ 15 suggests clinically significant impairment. Intervention Cross Talk will be assessed with 3 items from our previous studies that ask whether participants have talked with others about the intervention, how often, and about what content.

Other constructs shown to influence early adolescent sexual behavior will be measured to assess moderators of intervention impact.^{29, 134-140} Perceived Peer Approval (3 items)¹⁴¹ measures perceptions of peer approval of sexual behaviors ($\alpha = .81$). Normative Beliefs (5 items)¹⁴² assesses perceptions of peers' experience with and attitudes toward sexual behaviors ($\alpha = .76$). The Neighborhood Environment Scale (6 items)¹⁴³ assesses conditions of an adolescent's neighborhood ($\alpha = .83$).

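### The primary ANCOVA omits the randomization factors, school and gender; if they are prognostic beyond baseline, the unweighted analysis reports too wide a standard error

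*Combined protocol and SAP*

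**What the plan says.** The Randomization paragraph of Phase 2c says that "randomization will be stratified by school and gender and blocked using predetermined size-4 blocks". Human Subjects Involvement and Characteristics lists four schools, so there are eight strata if gender has two levels.

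The Data Analysis paragraph says "Analysis of covariance will be used to evaluate changes in self-efficacy for sexual risk prevention skills", with baseline as covariate. Under Primary Outcome, Statistical Design and Power says: "This outcome will be assessed using an analysis of covariance with baseline included as a covariate". The model is then reused: "Sexual health knowledge will be analyzed like the primary outcome", and the mechanism measures are assessed at 2 and 6 months "using analysis of covariance like for the primary outcome".

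The Data preparation paragraph plans inverse probability of treatment weights (IPTW) from covariate balancing propensity scores, where "the model will include demographics and baseline measures of primary outcomes, secondary outcomes, exploratory outcomes, moderators, and mechanisms". Gender may enter there as a demographic. Otherwise it appears only among the exploratory moderators: "Demographic information will be collected, allowing for analysis of demographic factors, including sex as a biological variable". No analysis names school as a covariate, stratum, random effect or weighting variable. The Primary Outcome paragraph does not mention weights, and no variance estimator is given for a weighted model.

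**The concern.** Blocking within strata balances the arms on school and gender, so differences between strata largely drop out of the treatment contrast. A model without those factors still counts the differences as residual noise. If they are real beyond what baseline explains, the reported standard error exceeds the true one, the interval is too wide and the test is conservative. At stake is some of the precision bought at randomization, for the primary outcome and for every outcome that reuses the model.

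**Working it through.** **Inputs from the documents.** N = 120, two-sided alpha .05, d = .47, baseline-to-6-month correlation r = .6, 10% expected attrition, four schools, blocks of 4. **Assumed.** Equal arms, two gender levels, and a strata share of 0, 5, 10 or 20% of the variance left after baseline. The 20% share is an upper-end case, since all four schools are in one district and baseline on the same scale is already in the model.

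**The plan's own figure.** The ANCOVA residual SD is sqrt(1 − .6²) = .8, so SE = .8 × sqrt(4/120) = .146. Then .47/.146 = 3.22, 3.22 − 1.96 = 1.26, and power is about .896 (.891 with the t distribution). The minimum detectable d is 2.80 × .146 = .409. The stated .80 at d = .47 is not reproduced and is conservative for the stated method. That is a separate matter, and nothing below depends on it.

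**Expected inflation.** If the strata explain a share R² of residual variance, reported SE / true SE ≈ 1/sqrt(1 − R²). This is 1.026, 1.054 and 1.118 at 5, 10 and 20%.

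**Simulation, unweighted, complete data.** 60,000 trials per setting, eight strata of 15, with the strata effect split equally between school and gender main effects. Paired entries are without / with strata terms; type I error is without.

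| Share | True SD of estimate | Mean reported SE | Type I error | Power at d = .47 |
|---|---|---|---|---|
| 0% | | | | .887 / .887 |
| 5% | .1436 / .1435 | .1465 / .1429 | .046 | .894 / .902 |
| 10% | .1391 / .1387 | .1465 / .1390 | .038 | .898 / .916 |
| 20% | .1326 / .1316 | .1467 / .1311 | .030 | .910 / .943 |

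Without strata terms the SE ratio is .1465/.1436 = 1.02, .1465/.1391 = 1.05 and .1467/.1326 = 1.11. The true SD barely changes when the terms are added; the reported SE is what moves. Smaller independent reruns gave type I error of .045, .039–.042 and .028–.030 without the terms, .047 to .054 with them, and power gains of 1 to 4 points. Unequal schools (48/36/24/12) gave the same 2, 5 and 11%.

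With 108 complete cases, power is .857/.863/.875 without and .867/.886/.919 with strata terms (.854 and .851 at 0%). This is only a rough guide, because the plan imputes missing outcomes and multiple imputation was not simulated.

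**Weights on gender and baseline only.** With an HC1 robust SE, the SE is still 4, 5 and 12% too wide, so weighting on gender does not cure the problem.

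**Full weight model.** The documents list 16 baseline scores besides the primary one: 2 cognition scales, 9 mechanism scores and 5 moderator scales. The Difficulties in Emotion Regulation Scale "uses six subscales (e.g., lack of emotional awareness, limited access to ER strategies". Counting these separately adds 5, and splitting the two self-regulation reports into short- and long-term scores adds 2, giving 23. Results treating the weights as fixed:

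- Covariates unrelated to outcome, no strata terms, shares 5–20%: type I error is .049 to .090 with the weighted model-based SE and .033 to .052 with HC1.
- Same covariates, 20% share, strata terms added: with 16 covariates the model-based SE goes from about .05 to .076 and HC1 from about .03 to about .058. With 23 they go from .072 to .096 and from .037 to .063.
- Covariates explaining 20% of residual variance (assumed), strata terms in: model-based .041 and .049 in two runs, HC1 .028–.038, HC3 .020 and .027.

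Monte Carlo error on type I error is about .001 for the unweighted runs and .002 for the 20,000-trial weighted runs.

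**Interaction.** If strata differ only through a school-by-gender interaction, main-effect terms do nothing: type I error was .043 and .044 in one check, and .037 with and without the terms in another.

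**The case against.** The strongest objection is that the plan calls for IPTW, so a result for the unweighted ANCOVA does not describe the planned analysis. This stands in part. The Primary Outcome paragraph leaves open whether the primary model is weighted, so the unweighted result is relevant, but its direction must not be attached to a weighted one. A reader might infer that the planned weighted analysis is conservative too. The documents do not support that, because the sign of the SE error depends on an unnamed variance estimator and on how prognostic the weight covariates are. Nor do they support the opposite inference that the weights already deal with stratification: school is not named in the weight model.

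A second objection is that adding strata terms is not free under weighting. This stands: the terms alone can lift a weighted model-based or HC1 test above .05.

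A third is that no strata effect is documented and the likely loss is small. This also stands. The shares are assumptions, the unweighted error is on the conservative side, and power is adequate. It bears on the size of the point but does not remove it, since at a zero share adding the terms costs essentially nothing.

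A fourth is that school and gender main effects assume additivity and two gender levels, neither of which the documents state for the strata. This stands and is carried into the fix.

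**Conclusion.** The omission is real: two factors define the randomization, the primary ANCOVA names neither, and school is absent from every analysis. For the unweighted ANCOVA the consequence is an SE about 2, 5 or 11% too wide and a loss of about 1, 2 or 3–4 points of power at assumed strata shares of 5, 10 or 20%. At 0% there is no loss.

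Two stronger conclusions are tempting and do not follow. The treatment estimate is not biased, and its true sampling variance is essentially the same with or without the strata terms. The trial is not underpowered on this account either, since power exceeds .80 in every unweighted case. For a weighted analysis no direction can be given until the variance estimator is named. The figures rest on the assumed shares, additive strata effects, two gender levels and equal arms.

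**What to change.** Add school (three indicators) and gender as fixed effects, alongside arm and baseline, to the primary ANCOVA and to its reuse for knowledge and the mechanism measures. If a school-by-gender interaction is plausible, use indicators for the stratum cells instead (4 × 2 − 1 = 7). If randomization uses more than two gender categories, the indicators should match them.

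For the unweighted ANCOVA this needs no new data. Residual degrees of freedom fall from 117 (120 less intercept, arm and baseline) to 113, or to 110 with cell indicators.

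If IPTW is kept, state whether the primary analysis is weighted, name the variance estimator, and simulate its type I error at N = 120 with the full weight model and the strata terms before the plan is final. The choice of estimator should follow from that check; the results here do not justify prescribing or prohibiting one in advance. The cost is a modest simulation. The opening note says that only Phase 1 is now submitted for approval, so both changes can be made before the RCT is submitted.
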